### 9.1. Overall Summary of Tolerability

An overall summary of tolerability table by treatment group and the two treatment groups combined for all subjects in the Safety Analysis Set will be produced.

The following statistics for the set of treated subjects will be displayed in this table:

- Subject months of study drug exposure descriptive statistics
- Number and percentage of subjects with treatment emergent adverse events (TEAEs)
- Number of TEAEs
- Number and percentage of subjects with serious adverse events (SAEs)
- Number and percentage of subjects with serious TEAEs
- Number and percentage of subjects requiring a dose alteration due to adverse events
- Number and percentage of subjects discontinuing the study due to adverse events
- Number and percentage of subjects who died

Another table displaying the same statistics by dosing sequence will be produced.

Subject months of drug exposure =

total number of days of treatment for each subject summed over all subjects divided by 30.4375

=

total duration of exposure in days for each subject summed over all subjects divided by 30.4375

See section 9.3 for the procedure used to calculate each subject's total duration of exposure (days) in this study.

To determine the number of adverse events, count all unique events reported at the preferred term level. Multiple events with the same preferred term are considered unique if the event onset dates are different.

## **9.2. Adverse Event Summary Tables**

Adverse events will be mapped to system organ class (SOC) and preferred term (PT) using MedDRA version 20.0.

An adverse event subject data listing providing a complete disclosure of adverse events as recorded in the CRF will be produced for each of the starting dose treatment groups.

To determine the number of adverse events, count all unique events reported at the preferred term level. Multiple events with the same preferred term are considered unique, if the event onset dates are different.

### **9.2.1. Summaries of All Treatment Emergent Adverse Events**

The summaries described below will be provided for the 24-Week Analysis and the Final Analysis.

1. The number and percentage of subjects with TEAEs will be summarized by MedDRA system organ class and preferred term within each starting dose treatment group and all treated subjects without regard to severity (intensity) or relationship to study drug. The SOCs will appear in descending order of number of subjects in the two treatment groups, i.e., all treated subjects, with at least one TEAE mapped to the SOC. The PTs within each SOC will appear in descending order of number of subjects in the two treatment groups with at least one TEAE mapped to the PT within that SOC
2. A table summarizing TEAE by intensity will be produced. The table will display the number and percentage of subjects with TEAEs summarized by MedDRA system organ class, preferred term, intensity level within each starting dose treatment group and all

treated subjects. The SOCs and PTs will appear in the same order as in the table described in #1 above.

3. A table summarizing TEAE by relationship to study drug will be produced. This table will display the number and percentage of subjects with TEAEs summarized by MedDRA SOC, PT and relationship to study drug within each starting dose treatment group and all treated subjects. The SOCs and PTs will appear in the same order as in the table described in #1 above.
4. Tables as described in #1, #2 and #3 above where, instead of the summaries for the two starting dose treatment groups, summaries are presented for the four dosing sequence treatment groups, Starting Dose Group Daily Dose (pills/day) – Week 12 Titrated Daily Dose (pills/day), i.e., 3 pills/day – 3 pills/day, 3 pills/day – 6 pills/day, 4 pills/day – 4 pills/day and 4 pills/day – 6 pills/day.
5. Tables displaying the number and percentage of subjects reporting serious AEs and the number and percentage of subjects reporting AEs leading to treatment discontinuation for all treated subjects and for each randomized dose group by MedDRA system organ class and preferred term.

Severity (Intensity on the eCRF) is classified as mild, moderate or severe where these categories denote increasing intensity, respectively. TEAEs starting after the first dose of study drug with a missing intensity will be classified as severe. If a subject has more than one TEAE within the same SOC/ PT, the AE with the worst case intensity will be used in the corresponding intensity summaries.

The only relationships of AE to study drug used in this study are “unrelated” and “related”. An AE’s relationship to study drug is based on the Investigator’s assessment. TEAEs with the relationship to study drug missing will be classified as “related” to study drug. If a subject has more than one AE within the same SOC and PT, the AE with the worst case relationship to study drug will be used in the corresponding relationship summaries.

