### 4.3. Sample Size Considerations

#### 4.3.1. Sample Size Justifications

Because this is an open-label Phase 4 study designed to estimate within-group changes from Baseline and describe time trends of iron parameters in subgroups of subjects, it is appropriate to conduct a precision-based sample size estimation as opposed to a power-based calculation. The primary endpoint of interest is change in Hgb from Baseline at Week 24. The standard deviation

(SD) for that endpoint is estimated as 0.9 g/dL based on the Week 16 data in a prior Phase 3 study in a similar population (Keryx Study KRX-0502-306).

Assuming a population SD of 0.9 g/dL, with a sample size of 140 subjects, the 95% confidence intervals (CIs) for mean change in Hgb from Baseline to Week 24 can be estimated, allowing for a CI half-width of 0.149 g/dL.

It is assumed that 30% of the subjects in this study will drop out or be otherwise excluded from the PP population. Hence, 200 subjects will be randomized to ensure that there will be sufficient subjects at the end of the study for the longitudinal analyses (i.e., 70 evaluable subjects in each randomized treatment group). Based on prior clinical trial experience, it is estimated that half of the subjects will stay on their starting dose, and the other half will increase their dose after 12 weeks of treatment. Hence, it is expected that the 4 dosing sequence groups that will arise will have approximately equal numbers of subjects (i.e., 35 subjects are expected in each of the four dosing sequence groups (3-3, 3-6, 4-4, and 4-6 tablets/day).

The proposed sample size and the sizes of the subgroups of interest are deemed sufficient for the analyses proposed below including the longitudinal analyses.

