#### **4.4. Randomization**

In this open-label study, eligible subjects will be randomized 1:1 to one of the two KRX-0502 starting dose groups with approximately 100 subjects per group:

- Group 1: KRX-0502 1 tablet TID (total of 3 tablets/day) with meals
- Group 2: KRX-0502 2 tablets BID (total of 4 tablets/day) with the largest 2 daily meals

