## 6.2. Data Presentation Conventions

Unless otherwise stated, all analyses will be performed using SAS® Version 9.4 or higher.

The following formats apply to all tables, figures and listings:

1. p-values will be presented with 3 decimals; p-values that are less than 0.001 will be presented as <0.001. If the rounded result is a value of 1.000, it will be displayed as >0.999. All date information in listings will be presented using 9 character alphanumeric formats (e.g., 01JAN2008).
2. Continuous data will be summarized using descriptive statistics: number of observations (n), mean, standard deviation (SD), median, 25th and 75th percentiles, minimum, and maximum. Given that the 25th and 75th percentiles are the 1st and 3rd quartiles, respectively, they will be labelled as Q1 and Q3, respectively.
3. Unless otherwise specified, in summary tables of continuous variables, the minimum and maximum values will be displayed to the same number of decimal places as the raw data, the mean and median will be presented to one extra decimal place compared to the raw data, and the standard deviation and coefficient of variation will be displayed to two extra decimal places compared to the raw data.
4. Frequencies and percentages will be used to summarize categorical (discrete) data. If there are missing values, the number missing will be presented.
5. Percentages will be based on the non-missing values. Presentations of categorical data will generally suppress percentages for items where the count is zero in order to draw attention to the nonzero counts.
6. Unless otherwise stated, confidence intervals, when presented, will be constructed at the two-sided 95% level.
7. For binomial variables, the confidence intervals will be constructed using the normal approximation without continuity correction due to the relatively large sample size.
8. Wherever possible, data will be decimal aligned.
9. Some laboratory values may be reported as <x, <=x, >x, or >=x due to the limits of detection for a specific assay, where x is the lower or upper limit of detection. For analysis purposes, these values will be treated as x, and for the listings they will be transcribed as from the raw data. (e.g., <x, <=x, >x, or >=x).
10. The listings that display Study Day will have its numeric value, with 'Day' appended as a prefix and a suffix (if applicable) that is:
  - F, if Study Day is the subject's first study medication dose date,

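### Adverse event tables by dosing sequence mix starting-dose events with events at 6 tablets/day, and no rule places subjects who stop before the Week 12 decision

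*SAP*

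**What the plan says.** **Sequence tables.** SAP 9.2.1 item 4 takes the TEAE tables of items 1 to 3 (overall, by intensity, by relationship) and replaces the starting-dose columns: "summaries are presented for the four dosing sequence treatment groups". Each column pairs the starting daily dose with the daily dose set at Week 12: 3-3, 3-6, 4-4 or 4-6. These tables are planned for both the 24-Week and the Final analysis. After listing the tolerability overview, which includes exposure and AE discontinuations, SAP 9.1 adds: "Another table displaying the same statistics by dosing sequence will be produced".

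**Event window.** SAP section 9 counts TEAEs from the first dose. No AE summary is divided at Week 12.

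**Group definition.** SAP 8.4, in the efficacy subgroup section, builds the sequence from the prescribed baseline dose and the Week 12 titration assignment. Protocol 15.7.2 builds it from the doses each subject actually took. SAP section 9 has no rule of its own.

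**Dose before Week 12.** Protocol 7.5 caps it at the dose set at randomization, 3 or 4 tablets/day.

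**Population.** SAP 6.3.3 puts anyone with at least one dose in the Safety Analysis Set, and its main safety grouping is the randomized starting dose.

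**The concern.** A subject's column is decided by a haemoglobin result at about Week 12, but the column is filled with events from first dose. In 3-6 and 4-6, every event before titration arose at 3 or 4 tablets/day and is pooled with events at 6. The study's stated aim includes the safety of different dose regimens, and a reader who wants to know how subjects fared after the increase has no other AE summary table to consult.

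The counting rules add to the mixing. Percentages count subjects, and SAP 9.2.1 keeps the worst intensity per preferred term. A subject with an event at 3 tablets/day who has it again at 6 adds nothing to the percentage, and a severe event before titration remains the 3-6 entry whatever follows.

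The second gap concerns subjects who stop before the decision. They belong to the Safety Analysis Set, but no column or rule is given for them. SAP 9.1 asks for AE discontinuations by sequence, so the undefined placement falls on the subjects who matter most for that row.

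**Working it through.** **1. The plan's own figures.** SAP 4.3.1 states: "Assuming a population SD of 0.9 g/dL, with a sample size of 140 subjects", "allowing for a CI half-width of 0.149 g/dL".
- Half-width = 1.96 × 0.9 / √140 = 0.149 g/dL, which reproduces.
- Randomized: 140 / 0.70 = 200, which reproduces.
- Per sequence: 200 × 0.70 / 4 = 35, which reproduces. It rests on 1:1 allocation and on the assumption that "it is estimated that half of the subjects will stay on their starting dose".

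The plan gives no precision figure for AEs, so what follows describes the tables' structure or is labelled as an assumption.

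**2. Share of follow-up at the starting dose in 3-6 and 4-6** (subject who completes, no interruptions):
- 24-Week tables: 12 / 24 = 50%
- Final tables: 12 / 48 = 25%

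3-3 and 4-4 have no planned dose change, so this part does not touch them.

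**3. What the mixing could do (assumed values).** Let f be the share of events expected before Week 12 at constant dose, and RR the true rate ratio of 6 tablets/day to the starting dose. Assume equal underlying risk in the columns being compared. The ratio seen in a 3-6 or 4-6 column is then f + (1 − f) × RR.

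| Assumed RR | 24-Week, f = 0.50 | Final, f = 0.25 |
|---|---|---|
| 1.5 | 1.25 | 1.375 |
| 2.0 | 1.50 | 1.75 |
| 3.0 | 2.00 | 2.50 |

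If events come early, with f of 0.60 to 0.75, an RR of 2.0 appears as 1.40 to 1.25. The documents give neither RR nor f.

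**4. Subjects who stop before the decision.** The only input is SAP 4.3.1: "It is assumed that 30% of the subjects in this study will drop out or be otherwise excluded from the PP population".
- Range allowed: 0 to 200 × 0.30 = 60 of 200.
- If all 30% were dropout spread evenly over 48 weeks: 200 × 0.30 × 12/48 = 15.
- If all 30% were dropout at constant hazard: 200 × (1 − 0.70^(12/48)) = 17.

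The last two are illustrations. The 30% also covers per-protocol exclusions, and no timing is given.

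**5. Why placement matters (assumed values).** Take 100 subjects on one starting dose, 8 AE stops before Week 12, and the other 92 split 46/46 with 5% later AE stops (2.3 per column).
- Early stoppers left out: 2.3 / 46 = 5.0% in both columns.
- Early stoppers put in 3-3 or 4-4: (2.3 + 8) / (46 + 8) = 19.1%, against 5.0% in 3-6 or 4-6.
- Whole starting-dose group: (4.6 + 8) / 100 = 12.6%.

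With 4 or 15 early stops, the second reading gives 12.3% or 29.8%.

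**6. Whether another rule fills the gap.** Protocol 7.5.1 handles a missing Week 12 haemoglobin by taking the first later value. That needs a subject who is still in the study, so it does not help.

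**The case against.** The strongest reply is that the columns are labelled as sequences. An event at 3 tablets/day in a 3-6 subject sits in a column that names 3 tablets/day. A reader might infer that the SAP assigns early events to the later dose and so misstates tolerability by dose. The labels do not support that; it follows only if a sequence column is read as a dose column. What stands is that the two dose levels are mixed and cannot be separated.

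A reader might also infer that early stoppers cannot appear in any column, or that the worst-tolerating subjects vanish from the safety analysis. Neither is established. Protocol 15.7.2 leaves room for 3-3 or 4-4. Item 4 replaces only the starting-dose columns, so an all-treated column may remain; the table shells are a separate document. The main overview in SAP 9.1, items 1 to 3 and 5 of 9.2.1, and the SAE, discontinuation and death tables in 9.2.3 are by starting dose and keep everyone treated.

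It is also true that AE and dosing listings exist, so individual events can be traced, and that Protocol 15.8 makes the sequence tables a supplement, to be produced if appropriate. Listings are not a summary, though, and the SAP does plan these tables.

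Finally, an onset split does not create a fair dose comparison, because titration depends on haemoglobin response and unscheduled reductions occur. That is correct and is the reason for a descriptive label.

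**Conclusion.** The point holds in a limited form. The 3-6 and 4-6 AE columns pool starting-dose and 6 tablets/day events, with 50% (24-Week) or 25% (Final) of a completer's planned follow-up at the starting dose. These are calendar shares, not estimates of bias. The placement of subjects who stop before the Week 12 decision is undefined, and the two documents' sequence rules point in different directions. How many subjects this affects cannot be derived beyond 0 to 60 of 200. A reader might take 15 of 200 as the expected number, but that treats the whole 30% as evenly spread dropout, which the documents do not say. The rate ratios and discontinuation percentages in the working rest on assumed inputs. The starting-dose AE tables are sound, so the overall safety conclusions do not depend on this; the description of tolerability after the increase does.

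**What to change.** In SAP 9.1 and 9.2.1 item 4:

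- Split the dosing-sequence AE tables by onset. By sequence, show TEAEs that start or worsen on or after the titration decision date, for subjects dosed after that date, with subject-months counted from it. For titrated subjects the date is the first day of the new dose; for the others it is the date of the Week 12 decision.
- Show pre-titration TEAEs by starting dose for the full Safety Analysis Set.
- Report, by starting dose, the number of subjects with no Week 12 assignment and their AE discontinuations.
- Reconcile the sequence definition in SAP 8.4 with Protocol 15.7.2, and state that it governs section 9.
- State how partial onset dates fall relative to the decision date. SAP 9.2.2 sets a completely missing date to first dose, and SAP 6.6.3 limits imputed dates to deciding treatment emergence.
- Label the sequence tables descriptive and not a randomized dose comparison.

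The cost is SAP wording, some table-shell work, a date filter on data already collected, and fewer events per sequence column.

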### **9.2.2. Missing and Partial AE Start Dates**

Completely missing or partially missing AE start (onset) dates will be imputed as follows:

- If onset date is completely missing, onset date is set to date of first dose.
- If (year is present and month and day are missing) or (year and day are present and month is missing):
  - If year = year of first dose, then set month and day to month and day of first dose
  - If year < year of first dose, then set month and day to December 31st

- If year > year of first dose, then set month and day to January 1st
- If month and year are present and day is missing:
  - If year=year of first dose and
    - if month = month of first dose then set day to day of first dose date
    - if month < month of first dose then set day to last day of month
    - if month > month of first dose then set day to 1st day of month
  - if year < year of first dose then set day to last day of month
  - if year > year of first dose then set day to 1st day of month
- For all other cases, set onset date to date of first dose

Note, adverse event listings will display start and end dates as collected, not imputed.

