In addition to the laboratory assessments listed above, the safety assessments schedule includes the following:

- AEs will be collected starting at the time of informed consent.
- Vital signs (seated heart rate and blood pressure after at least 5 minutes of rest) will be recorded at Visit 1A (Screening) and, if applicable Visit 1B (Re-screening); Visit 2 (Randomization); and all subsequent visits.

- Weight and height will be measured at Visit 1A (Screening) and, if applicable, Visit 1B (Re-screening). Weight will also be measured at Visit 2 (Randomization), Visit 9 (Week 24), Visit 12 (Week 48), and ET Visit.
- Spot urine protein-to-creatinine ratio will be measured at Visit 2 (Randomization).
- Serum pregnancy test for all women of childbearing potential will be performed at Visit 1A (Screening) and, if applicable, Visit 1B (Re-screening).

Further, serum samples that will be frozen for future analysis of biomarkers of CKD will be obtained at Visit 2 (Randomization), Visit 9 (Week 24), Visit 12 (Week 48), and the ET visit from only those subjects who provided informed consent specifically for their collection.

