### **6.6.3. Missing Start and Stop Dates for Adverse Events**

Missing stop dates for adverse events will not be imputed. Missing start dates for adverse events will be imputed in accordance with the rules specified in section 9.2.2. Imputed dates will only be used to determine whether an adverse event is treatment emergent or not.

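### The AE onset imputation in SAP 9.2.2 ignores the recorded stop date, so an event that ended before the first dose can be flagged as treatment-emergent when its onset is missing or known only to the first-dose year or month

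*SAP*

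**What the plan says.** SAP 6.6.3 gives the imputed onset one purpose: "Imputed dates will only be used to determine whether an adverse event is treatment emergent or not". It mentions AE stop dates only to say "Missing stop dates for adverse events will not be imputed".

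The rules in SAP 9.2.2 take two inputs, the known parts of the onset date and the first-dose date. Four branches end on the first-dose date:

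- No onset date: "If onset date is completely missing, onset date is set to date of first dose".
- Month missing, year known: "If year = year of first dose, then set month and day to month and day of first dose".
- Day missing, year equal to the first-dose year: "if month = month of first dose then set day to day of first dose date".
- Anything left over: "For all other cases, set onset date to date of first dose".

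An onset known to lie in an earlier month or year is placed before the first dose. Within the first-dose year, for example, "if month < month of first dose then set day to last day of month".

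SAP 9 defines a TEAE as an event that begins, or a pre-existing condition that worsens, after the first administration. If the eCRF data and/or the imputation procedure leave the status undetermined, the event counts as a TEAE.

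On collection, SAP 4.5 says "AEs will be collected starting at the time of informed consent". Protocol 13.2.2 has the investigator report for each AE an onset date and either a resolution date or that it is ongoing.

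**The concern.** There is a real pre-dose interval in which AEs are recorded, and some of those events will resolve before dosing starts. Once the recorded stop date precedes the first dose, the event cannot have begun after it, whatever the onset was. The data that settle the question are in the database, but the rule does not use them. It can give the event an onset later than its own end and call it treatment-emergent.

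At stake is the accuracy of the safety tables. Followed as written, the rule adds pre-treatment events to the number of TEAEs and to the subjects counted with a TEAE (SAP 9.1), and to the system organ class/preferred term and intensity tables, including those by dosing sequence (SAP 9.2.1). Since the imputed date exists only to set this flag, the flag is the whole of what can go wrong.

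**Working it through.** The plan states no figure on this point, so there is none to reproduce. The check applies the rules as written to hypothetical AEs that both began and ended before the first dose.

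**One event.** First dose 20 June 2018, recorded stop 10 June 2018:

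| Recorded onset | Imputed onset | Flag |
|---|---|---|
| none | 20 June 2018 | TEAE, onset 10 days after stop |
| 2018 | 20 June 2018 | TEAE, onset 10 days after stop |
| June 2018 | 20 June 2018 | TEAE, onset 10 days after stop |
| May 2018 | 31 May 2018 | not TEAE |
| 2017 | 31 December 2017 | not TEAE |

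**Inputs for the shares.**

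- Pre-dose window W. Consent up to 7 days before Screening (Protocol 10.1.1), randomization up to 21 days after Screening (Protocol 10.1), dosing the day after randomization (Protocol 7.5): 7 + 21 + 1 = 29 days. Shorter cases: 21 + 1 = 22, and 21.
- Assumed: first-dose dates spread evenly over the 365 days of 2018. Onset falls 1 to W days before the first dose and the stop lies between onset and the day before the first dose, with every onset-stop pair equally likely. That gives W(W+1)/2 pairs per first-dose date: 435 for W = 29, 231 for W = 21.
- An imputed onset on or after the first-dose date is taken as a TEAE.

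**Onset completely missing.** Every event goes to the first-dose date: 100%.

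**Only the year known.** The flag is right only if the onset was in the previous year. For a first dose on day d of the year, d ≤ W, the pairs with onset in the same year number d(d-1)/2, and over d = 1 to W these sum to (W-1)W(W+1)/6.

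- W = 29: 28 × 29 × 30 / 6 = 4,060. Misclassified: 1 - (29 - 4,060/435)/365 = 1 - 19.67/365 = 94.6%.
- W = 21: 20 × 21 × 22 / 6 = 1,540. Misclassified: 1 - (21 - 1,540/231)/365 = 1 - 14.33/365 = 96.1%.

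**Only the day missing.** The flag is wrong when the onset falls in the first-dose month. For a first dose on day d of the month that is m(m+1)/2 pairs, with m the smaller of d-1 and W. Summing over months of 31, 30 and 28 days:

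- W = 29: (7 × 4,930 + 4 × 4,495 + 3,654) / (365 × 435) = 56,144 / 158,775 = 35.4%.
- W = 21: (7 × 3,850 + 4 × 3,619 + 3,157) / (365 × 231) = 44,583 / 84,315 = 52.9%.

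| Onset recorded as | W = 21 | W = 22 | W = 29 |
|---|---|---|---|
| nothing | 100% | 100% | 100% |
| year only | 96.1% | 95.9% | 94.6% |
| month and year | 52.9% | 50.7% | 35.4% |

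**With a stop-date condition.** Every event in this exercise has a stop date before the first dose, so none becomes a TEAE: 0% in each cell.

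**Date order.** With only the day missing, the imputed onset falls after the stop date in 66.0% (W = 29) to 74.8% (W = 21) of these events. The excess over 35.4% and 52.9% is events placed at the end of an earlier month: their dates are out of order but the flag is right.

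All these shares are conditional on the event having ended before dosing and on the stated onset pattern.

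**The case against.** **SAP 9 already allows the right answer.** It bases classification on the eCRF data and/or the imputation procedure. The resolution date is eCRF data, and an event that ended before dosing cannot meet the TEAE definition. This stands in part: a careful programmer could classify such events correctly, so miscounting is not certain. But nothing says that a pre-dose stop date overrides the imputed onset, and the specific rule in 9.2.2 points the other way. By contrast, SAP 7.5 does use stopping before the first dose to define prior medications.

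**The imputed onset equals the first-dose date, and a TEAE must begin after it.** Read that strictly and the affected events are non-emergent or unresolved, and SAP 9 sends unresolved ones to TEAE. Imputing to that date is evidently meant to make the event treatment-emergent.

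**The default is deliberately cautious.** It matches other SAP defaults, such as counting a missing relationship as related (9.2.1). The direction is indeed cautious, both groups take the same drug after the same screening, and no between-group bias is shown. But caution is the reason for a default when status is unknown, and here it is known.

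**The impossible date goes nowhere.** This stands. Listings show dates as collected, so affected events remain visible there.

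**Stronger readings a reader might infer.** One is that drug-related TEAEs are inflated. Protocol 13.2.2.2 treats an event as unrelated when the subject has not received study drug, so a false TEAE enters the related counts only if the relationship is missing or was recorded as related. Another is that serious TEAEs are materially affected. Protocol 10.3 has sites verify before randomization that the subject has not required hospitalization since Screening, and Protocol 13.2.3 requires SAE reports within 24 hours, so a serious screening event with a missing onset should be rare in a treated subject. A third is that every screening AE with a partial onset is miscounted, but an onset known to an earlier month or year is classified correctly.

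**Conclusion.** The point holds as a minor defect in a stated rule. Applied literally, SAP 9.2.2 flags an AE as treatment-emergent despite a recorded stop date before the first dose when the onset is completely missing, known only to the first-dose year, known only to the first-dose month, or caught by the final branch. The effect is an overcount of TEAEs. Each affected record adds one to the event count. The tables that count subjects change less, because a subject who has another TEAE under the same preferred term adds nothing there.

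The overall size cannot be quantified from the documents. It is expected to be small, because the event must combine a missing or partial onset of the right kind with a stop date before dosing. A reader might take 29/(29 + 337) = 7.9% as the share of AEs starting before dosing, multiply by an assumed 2-10% of partial onsets, and treat the resulting 0.2-0.8% as a ceiling. The documents do not support that:

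- The partial-date rate is not in them.
- Re-screening at least 2 weeks after a screen failure (Protocol 10.2) can stretch the interval from consent beyond 29 days, and the actual first dose may differ from the prescribed day (SAP 6.4).
- The 337 days, the Week 48 target day, suppose that everyone completes, while SAP 4.3.1 assumes 30% drop out or are otherwise excluded from the Per Protocol population.
- The product leaves out the need for a pre-dose stop date and an affected onset pattern.

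The conditional shares under the working rest on its even-spread assumptions. That the flag is wrong for such an event does not.

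**What to change.** Change SAP 9.2.2 in two places.

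1. Before the imputation steps, add: *If the recorded AE stop date, or its known parts, establish that the AE ended before the first dose date, the AE is not treatment-emergent.* A partial stop date in the first-dose month does not establish this by itself.
2. After the imputation steps, add: *If the imputed onset is later than a complete recorded stop date, set the onset to the stop date.* This keeps the derived dates in order. The first sentence already corrects the flag.

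Keep the existing default to TEAE for events whose stop date is missing or does not settle the question.

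The cost is two sentences in the SAP and the matching lines of code. No new data are needed, since the resolution date is already collected.
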